8.1.11 Participant Blinding/Unblinding

STUDY INTERVENTION IDENTIFICATION INFORMATION IS TO BE UNMASKED ONLY IF NECESSARY FOR THE WELFARE OF THE PARTICIPANT. EVERY EFFORT SHOULD BE MADE NOT TO UNBLIND.

For emergency situations where the investigator or medically qualified designee (consistent with local requirements) needs to identify the intervention used by a participant and/or the dosage administered, he/she will contact the emergency unblinding call center by telephone and make a request for emergency unblinding. As requested by the investigator or medically qualified designee, the emergency unblinding call center will provide the information to him/her promptly and report unblinding to the Sponsor. Before contacting the emergency unblinding call center to request unblinding of a participant's intervention assignment, the investigator who is a qualified physician should make reasonable attempts to enter the intensity of the AEs observed, the relation to study intervention, the reason thereof, etc, in the medical record. If it is not possible to record this assessment in the medical record before the unblinding, the unblinding should not be delayed.

If unblinding has occurred, the circumstances around the unblinding (eg, date, reason, and person performing the unblinding) must be documented promptly, and the Sponsor Clinical Director notified as soon as possible.

Once an emergency unblinding has taken place, the investigator, site personnel, and Sponsor personnel may be unblinded so that the appropriate follow-up medical care can be provided to the participant.

Participants whose treatment assignment has been unblinded by the investigator or medically qualified designee and/or nonstudy treating physician must be discontinued from study intervention, but should continue to be monitored in the study.

Additionally, the investigator or medically qualified designee must go into the IRT system and perform the unblind in the IRT system to update drug disposition. If the emergency unblinding call center is not available for a given site in this study, the IRT system should be used for emergency unblinding if this is required for participant safety.

At the end of the study, random code/disclosure envelopes or lists and unblinding logs are to be returned to the Sponsor or designee.

8.1.12 Calibration of Equipment

The investigator or qualified designee has the responsibility to ensure that any device or instrument used for a clinical evaluation/test during a clinical study that provides information about inclusion/exclusion criteria and/or safety or efficacy parameters shall be suitably calibrated and/or maintained to ensure that the data obtained are reliable and/or reproducible. Documentation of equipment calibration must be retained as source documentation at the study site.

8.1.13 PK/PD/Biomarker Subpopulation

At selected sites, additional PK/PD/Biomarker samples will be collected from >15 participants per treatment arm, as outlined in the SoA (Section 1.3.3), in addition to the samples listed in the Double-Blind Treatment and Blinded Extension Periods (Sections 1.3.1 and 1.3.2).

The purpose of the Subpopulation is to provide additional PK and PD measurements, allowing a more comprehensive characterization of the PK-PD relationship of MK-6194. The additional PD and biomarker sample collection is to enable Treg and other biomarker assessments at more timepoints, to allow better understanding of PD and biomarker responses to MK-6194 in participants with vitiligo.

8.2 Efficacy Assessments

8.2.1 PROs

All PROs should be completed in the order listed in the SoA *before* laboratory tests or any other efficacy or safety procedures, except for Visit 2 (Randomization) where PROs can be completed after confirming eligibility. Participants will be trained by site personnel on the use of an electronic tablet for PRO completion and are to complete the questionnaires on their own at the study site using the provided electronic tablet.

VitiQoL

The VitiQoL is a 16-item validated, disease-specific instrument that measures the impact of vitiligo on patients' social, emotional and physical functioning [Lilly, E., et al 2013]. Items are scored using a 7-point Likert scale (0 – 6), with lower scores indicating better quality of life.

Vitiligo Noticeability Scale

The VNS is a single-item measure that asks patients to rate the noticeability of their vitiligo compared with before they started treatment on a 5-point scale ranging from 1 (more noticeable) to 5 (no longer noticeable). Scores of 4 – 5 are considered indicative of treatment success.

Patient Global Impression of Severity

The PGI-S is a 2-item measure asking the participant to rate the severity of their vitiligo on their facial area and on their total body area right now, with response options of none, mild, moderate, severe, and very severe.

Patient Global Impression of Change/Meaningfulness

The PGIC/M is a 2-part measure asking the participant to rate the change in their vitiligo since they started taking the study medication, with response options ranging from “much better” to “much worse”. Based on the response to the initial question, the participant is

asked a follow-up question to evaluate the meaningfulness of the improvement or worsening, with response options of “yes” or “no” indicating whether the improvement or worsening was important to the participant or not.

8.2.2 ClinROs

All ClinROs should be completed in the order listed in the SoA. The investigator or medically qualified designee are to complete the questionnaires using the provided electronic tablet. Separate instructions on how to complete the ClinROs will be available if needed.

Investigator qualifications, training, and applicable certification processes are established in a separate document. It is strongly encouraged that the same investigator evaluates the same participant for the duration of the study to improve continuity and reliability of the assessments.

Clinical Global Impression of Severity

The CGI-S is a 2-item measure asking the investigator to rate the severity of participant’s vitiligo on their facial area and on the total body area right now, with response options of none, mild, moderate, severe, and very severe.

Clinical Global Impression of Change

The CGI-C is a 2-item measure asking the investigator to rate the change in the participant’s vitiligo on their facial area and on the total body area since they started taking the study medication, with response options ranging from “much better” to “much worse”.

Facial Vitiligo Area Scoring Index (F-VASI) and Total Vitiligo Area Scoring Index (T-VASI)

The VASI is a validated scoring method that assesses the extent and severity of areas of vitiligo depigmentation. There are 2 region-specific VASI scores that will be calculated for the study; the F-VASI, which measures vitiligo involvement of the facial area, and the T-VASI, which measures vitiligo involvement for the total body. Both are scored by measuring the total area of depigmentation, as measured by a standard unit, multiplied by the percent of depigmentation of the affected areas.

F-VASI is defined as the sum of the area(s) of all vitiligo lesions on the Face X Average Degree of Depigmentation (%).

The FACE is defined as the area between the hairline, chin, and up to the ears. This area includes the eyelids, cheeks, and nose, but DOES NOT INCLUDE the lips, scalp, ears, or neck.

Vitiligo lesions on face will be estimated by using a fingertip unit (1 FTU), a finger (3 FTUs), or a thumb (3 FTUs) depending on the lesion size. One FTU is equivalent to 0.03% of the body surface area (BSA) and a finger and thumb are considered 0.1% BSA. The degree of depigmentation for each vitiligo involvement site is determined and estimated to

the nearest of the following percentages: 0% (no depigmentation), 10%, 25%, 50%, 75%, 90%, or 100% (complete depigmentation). The F-VASI is derived by multiplying the values assessed for the vitiligo involvement by the percentage of affected skin for each site on the face and summing the values of all sites together. Possible scores range from 0-3.5.

The T-VASI determines the degree of vitiligo involvement of the whole body. The total body is separated into 6 mutually exclusive areas: 1. Head/Neck (Including the Face), 2. Hands, 3. Upper extremities (Excluding the hands), 4. Trunk (Including genitalia; Excluding buttocks), 5. Lower extremities (Including buttocks; Excluding the feet), and 6. Feet. The area of depigmentation will be measured by using the palmar method, whereupon one hand unit (comprised of the patient's palm + 5 digits, with fingers tucked together & thumb tucked to the side) = 1% Body Surface Area. As for the F-VASI, the degree of depigmentation for each vitiligo involvement site is determined and estimated to the nearest of the following percentages: 0% (no depigmentation), 10%, 25%, 50%, 75%, 90%, or 100% (complete depigmentation). Where there are multiple lesions within a body region, the degree of depigmentation within each body region should be estimated using the above percentages and then averaged to the closest overall percentage. For example, if there are 3 vitiligo lesions within a body region, with degrees of depigmentation of 75%, 50% and 100%, the estimated average degree of depigmentation for that region would be 75%.

The area of percent depigmentation scores for each body region are summed to derive the T-VASI score, which ranges from 0 to 100, with 0 indicating no vitiligo and 100 indicating vitiligo on the entire body. Note that, when a lesion crosses over more than one region, the scoring for the lesion is not split between regions; the investigator will select one of the regions to include that lesion in to calculate the VASI for that region, always including that lesion in the same region for all future assessments.

Body Surface Area

The participant's right or left hand should be selected as the measuring device. For purposes of clinical estimation, the total surface of the palm plus 5 digits, with fingers tucked together and thumb tucked to the side, will be assumed to be approximately equivalent to 1% BSA. Measurement of the total area of involvement by the physician is aided by clinical judgment (ie, if specks of pigment were moved so that they were next to each other and then estimating the total area involved). The site should make every attempt to have the same qualified investigator or designee perform all BSA assessments on a given participant throughout the study.

CCI

8.2.3 Photography

Photography of the face and/or body areas affected with vitiligo will be obtained at the times outlined in the SoA using the provided electronic tablet to support the F-VASI, T-VASI, and CCI Photographs will be anonymized to the extent possible in order to protect participant's identity. Additional instructions and a full description of the methodology for obtaining photographs are provided in a separate manual. Photographs will not be used for formal assessments of efficacy; however, may be included in the CSR or other publications.

The F-VASI and T-VASI photographs will be reviewed centrally; however, it is the investigator's VASI score that will be used for efficacy calculations. If the photographs obtained at Screening are deemed sufficient by the central reviewer, no additional photographs are required at the randomization visit.

8.3 Safety Assessments

Details regarding specific safety procedures/assessments to be performed in this study are provided. The total amount of blood/tissue to be drawn/collected over the course of the study (from prestudy to poststudy visits), including approximate blood/tissue volumes drawn/collected by visit and by sample type per participant, can be found in the Laboratory Manual.

Planned time points for all safety assessments are provided in the SoA.

8.3.1 Physical Examinations

A full physical examination will be conducted by an investigator or medically qualified designee (consistent with local requirements) per institutional standard at the visits listed in the SoA.

The full examination should be based on the following body systems: general appearance, head (oral inspection, ears, eyes, nose, and throat), respiratory (auscultation/stethoscopy examination of the lungs), heart (auscultation/stethoscopy examination of the heart), abdomen, musculoskeletal, neurological, lymph nodes, and skin (rash, injection site). Other body systems may be examined at the discretion of the investigator.

Note that a urinary/genital examination is not required; however, visual inspection of the urinary/genital area for areas of depigmentation is expected.

Height and body weight will be measured and recorded per the SoA, and will be obtained with the participant's shoes off and jacket or coat removed.

Physical findings at Screening will be recorded as medical history. Abnormal findings that are worsening of a baseline finding or any new abnormal findings from other visits will be recorded as an AE.

A brief directed physical examination will be conducted by an investigator or medically qualified designee (consistent with local requirements) per institutional standard at the visits listed in the SoA.

A physical examination (full or limited, based on investigator judgment) can be performed at any unscheduled visit if deemed necessary by the investigator. Investigators should pay special attention to clinical signs related to previous serious illnesses.

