8.1.4 Medical History

A medical history will be obtained by the investigator or qualified designee at the Screening Visit. Participants will be asked to provide any background or concomitant conditions, drug allergies, surgical procedures, or other medical conditions. Additionally, a complete vitiligo medical history will be collected.

Clinically significant findings in physical examination, laboratory tests, ECGs, and other physical evaluations during Screening are to be noted in the medical history. Clinically significant changes from the Screening evaluation during the study should be captured as AEs.

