8.4.6 Disease-related Events and/or Disease-related Outcomes Not Qualifying as AEs or SAEs

Not applicable

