10.3.2 Definition of AE

AE definition

- An AE is any untoward medical occurrence in a clinical study participant, temporally associated with the use of study intervention, whether or not considered related to the study intervention.
- Note: An AE can therefore be any unfavorable and unintended sign (including an abnormal laboratory finding), symptom, or disease (new or exacerbated) temporally associated with the use of a study intervention.
- Note: For purposes of AE definition, study intervention includes any pharmaceutical product, biological product, vaccine, diagnostic agent, medical device, combination product, or protocol-specified procedure whether investigational or marketed (including placebo, active comparator product, or run-in intervention), manufactured by, licensed by, provided by, or distributed by the Sponsor for human use in this study.

Events meeting the AE definition

- Any abnormal laboratory test results (hematology, clinical chemistry, or urinalysis) or other safety assessments (eg, ECG, radiological scans, vital signs measurements), including those that worsen from baseline, considered clinically significant in the medical and scientific judgment of the investigator.
- Exacerbation of a chronic or intermittent preexisting condition including either an increase in frequency and/or intensity of the condition.

- New conditions detected or diagnosed after study intervention administration even though it may have been present before the start of the study.
- Signs, symptoms, or the clinical sequelae of a suspected drug-drug interaction.
- Signs, symptoms, or the clinical sequelae of a suspected overdose of either study intervention or a concomitant medication.
- For all reports of overdose (whether accidental or intentional) with an associated AE, the AE term should reflect the clinical symptoms or abnormal test result. An overdose without any associated clinical symptoms or abnormal laboratory results is reported using the terminology “accidental or intentional overdose without adverse effect.”
- Any new cancer or progression of existing cancer.

Events NOT meeting the AE definition

- Medical or surgical procedure (eg, endoscopy, appendectomy): the condition that leads to the procedure is the AE.
- Situations in which an untoward medical occurrence did not occur (social and/or convenience admission to a hospital).

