- Anticipated day-to-day fluctuations of preexisting disease(s) or condition(s) present or detected at the start of the study that do not worsen.
- Surgical procedure(s) planned prior to informed consent to treat a preexisting condition that has not worsened.
- Refer to Section 8.4.6 for protocol-specific exceptions.

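### AE recording thresholds conflict between sections, and vitiligo worsening is not excepted, so lack of efficacy can enter the aggregate safety rows

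*Protocol*

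**What the plan says.** AEs and discontinuation due to AEs are the endpoints of a primary objective (Protocol Section 3). Several places govern what is recorded:

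- **Section 8.3.1:** "Abnormal findings that are worsening of a baseline finding or any new abnormal findings from other visits will be recorded as an AE". It contains no test of clinical significance. The same section notes that "visual inspection of the urinary/genital area for areas of depigmentation is expected".
- **Section 8.1.4**, covering physical examination, laboratory and other evaluations: "Clinically significant changes from the Screening evaluation during the study should be captured as AEs".
- **Section 10.3.2, item on laboratory results and other safety assessments:** abnormal results count if they are "considered clinically significant in the medical and scientific judgment of the investigator".
- **Section 10.3.2, item on preexisting disease:** "Exacerbation of a chronic or intermittent preexisting condition including either an increase in frequency and/or intensity of the condition". This item carries no significance test.
- **Section 10.3.2, exclusions:** ordinary variation in a preexisting disease is exempt only while the disease does not get worse. The list ends "Refer to Section 8.4.6 for protocol-specific exceptions".
- **Section 8.4.6**, headed "Disease-related Events and/or Disease-related Outcomes Not Qualifying as AEs or SAEs", reads "Not applicable".

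SAP Section 3.5.3.1 and its Table 3 give between-group 95% CIs for any AE, serious AE, drug-related AE, serious drug-related AE and discontinuation due to AE. They also give CIs for each specific AE or organ class that reaches 4 participants in any group. No row leaves out worsening of the disease under study.

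**The concern.** There are two problems.

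First, the same examination finding can be an AE under 8.3.1 and not under 8.1.4. AE counts then depend partly on which section a site follows.

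Second, every participant enters with depigmentation (Section 5.1 requires F-VASI of at least 0.3 and T-VASI of at least 4). Randomization is stratified by active disease, which includes new or extending lesions in the 6 months before Screening (Section 6.3.2). Worsening is therefore foreseeable, and under 10.3.2 it is an AE. It is also the opposite of the efficacy outcome. If the drug works, placebo collects more of these events, and any aggregate containing them understates the drug's excess of other AEs. At stake is whether the aggregate rows of a primary safety endpoint can be read as harm, separately from lack of efficacy.

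**Working it through.** **The plan's own figure.** SAP 3.5.3.1 sets the threshold of 4 participants because, below it, the CI for a difference always includes zero. With 55 per arm (Protocol 9.8) and the Miettinen-Nurminen score interval:

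- 3 v 0 gives -1.3 to 14.9 points, which includes zero.
- 4 v 0 gives 0.5 to 17.3 points, which excludes it.

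The threshold reproduces.

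**Reading the text.** Take a participant whose facial patch has grown since Screening.

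| Rule | Is it an AE? |
|---|---|
| 8.3.1 | Yes, as worsening of a baseline finding |
| 8.1.4 | Only if clinically significant |
| 10.3.2, safety-assessment item | Only if judged clinically significant |
| 10.3.2, exacerbation item | Yes, with no significance test |
| 10.3.2, fluctuation exemption | Does not apply, because the disease has worsened |
| 8.4.6 | No exception given |

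The first three rows conflict. The last three make vitiligo worsening an AE whatever is done about the first three.

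**Effect on the any-AE row.** Let p be the rate of other AEs and w the rate of recorded vitiligo worsening, assumed independent. Then:

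any-AE rate = 1 - (1 - p)(1 - w)

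The documents give neither p nor w. All rates in this table are assumptions, with p = 60% on MK-6194 and 50% on placebo.

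| w, MK-6194 / placebo | MK-6194 | Placebo | Difference |
|---|---|---|---|
| 0 / 0 | 60.0% | 50.0% | +10.0 |
| 5% / 15% | 1 - 0.40 x 0.95 = 62.0% | 1 - 0.50 x 0.85 = 57.5% | +4.5 |
| 8% / 20% | 1 - 0.40 x 0.92 = 63.2% | 1 - 0.50 x 0.80 = 60.0% | +3.2 |
| 5% / 30% | 62.0% | 1 - 0.50 x 0.70 = 65.0% | -3.0 |
| 15% / 15% (no efficacy) | 1 - 0.40 x 0.85 = 66.0% | 57.5% | +8.5 |

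Without efficacy the difference is only diluted, by the factor 1 - w.

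**A scenario tied to the planning figures.** Protocol 9.8 assumes an effect of -20 and an SD of 33 in percent change of F-VASI. Assume normality and a placebo mean of 0. The chance that F-VASI rises is then 50% on placebo and 1 - Φ(20/33) = 27.2% on MK-6194. Take other AEs at 50% on placebo and 70% on MK-6194, a true difference of 20 points:

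| Share of worsenings recorded as AEs | Placebo | MK-6194 | Difference |
|---|---|---|---|
| 10% | 52.5% | 70.8% | +18.3 |
| 50% | 62.5% | 74.1% | +11.6 |
| 100% | 75.0% | 78.2% | +3.2 |

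F-VASI at Week 24 is only a proxy, since it leaves out body lesions.

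**Term-level rows.** A separate term does not move. For example, injection-site reaction in 10 v 2 of 55 gives 3.2 to 27.3 points whether or not vitiligo events are counted elsewhere. In the first table's unequal scenarios, placebo worsening is 0.15 x 55 = 8.25, 0.20 x 55 = 11 and 0.30 x 55 = 16.5 participants. All exceed 4, so coded to one term it would already have its own CI. It loses that CI if no group exceeds 3 of 55 (5.5%). The distortion is then small: 3 v 0 shifts the first table's difference by at most 0.50 x 3/55 = 2.7 points. Worsening split over several terms could add up to more with no CI shown.

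**The case against.** The strongest reply is that counting disease worsening as an AE is a recognisable conservative choice, and that 8.4.6 was answered rather than overlooked. Further:

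- The skin item of the examination names rash and injection site, and 8.3.1 mentions depigmentation only for the genital area. Vitiligo extent is measured as efficacy under 8.2.2.
- After Screening, the double-blind schedule has a full examination only at Week 24 or discontinuation; other examinations are directed.
- Recording detail is left to data entry guidelines outside these documents.
- SAP 3.5.3.1 treats unadjusted safety CIs as descriptive, and eosinophil and liver criteria are also reported as events of clinical interest (8.4.7).
- SAP 3.5.2 lists lack of efficacy apart from AEs among reasons for discontinuation.

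Most of this stands, and it limits the point to aggregates. It does not remove it. The exacerbation item of 10.3.2 applies however the worsening is found. The SAP's list of reasons concerns leaving the study and gives no rule for coding a participant who stops treatment because vitiligo has spread.

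A reader might infer that every new patch will be recorded and that harm will be masked. The documents do not support that: 8.1.4 and part of 10.3.2 apply a significance test, individual terms are untouched, and the shift needs efficacy. A reader might also infer that sites following 8.1.4 and 10.3.2 would not record vitiligo worsening at all. That fails too, because the exacerbation item has no such test.

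**Conclusion.** The point holds in limited form. The recording threshold is inconsistent between 8.3.1 and 8.1.4 with part of 10.3.2. Separately, vitiligo worsening is an AE as the protocol is written, so lack of efficacy enters the any-AE row, possibly the skin organ-class row and, where so coded, discontinuation due to AE. If MK-6194 works, the shift favours the drug.

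The size cannot be fixed from the documents. Under the assumed rates, a true +10 points falls to between +4.5 and -3.0, and a true +20 to between +18.3 and +3.2. The sign reversal needs a 5% v 30% split that nothing in the documents supports. These figures rest on assumed AE rates, independence, efficacy and the share of worsening recorded. Sample size, alpha and power for the primary efficacy test are unaffected. A correction is worth making because it is cheap and concerns a primary endpoint.

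**What to change.** 1. **Protocol 8.3.1, 8.1.4 and 10.3.2:** reconcile them so that one threshold applies to examination findings. Adding a significance test to 8.3.1 alone would not settle the vitiligo question, because the exacerbation item would still apply.
2. **Protocol 8.4.6:** state how worsening of vitiligo is to be recorded, including how a stop of study intervention for that reason is coded.
3. **SAP 3.5.3.1:** prespecify, before unblinding, the list of vitiligo-worsening terms. Repeat the any-AE, drug-related AE and discontinuation-due-to-AE rows without them. Show those terms by arm whether or not they reach 4 participants.

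No data are lost and worsening stays visible by arm. The cost is a few sentences in the protocol, a term list and a second AE overview table to report and explain.
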